5. Assess HIV testing and STI screening patterns at index oral or LA PrEP initiation and within 12-months following index PrEP initiation among people who initiate a PrEP regimen
6. Describe demographic and clinical characteristics, HIV testing and diagnoses, as well as STI screening and diagnoses over a 12-month period of follow-up among people who are not on PrEP but could benefit from PrEP

Study Design

Design: Cohort study using secondary data from electronic medical records in the OPERA cohort.

Exposure groups: Oral PrEP, LA PrEP

Duration of study:

- Analysis #1: 2021 to 2023 (Obj 1-1a); 21DEC2021 to 30JUN2024 (Obj 2-6)
- Analysis #2: 2021 to 2024 (Obj 1-1a); 21DEC2021 to 30JUN2025 (Obj 2-6)

Population

(Obj 1) People in OPERA aged ≥ 18 years with ≥ 1 clinical encounter during the calendar year of interest and no evidence of prior HIV diagnosis.

(Obj 1a) People with an incident HIV diagnosis identified in Obj 1.

(Obj 2-5) People without HIV in OPERA aged ≥ 18 years who initiated any new PrEP formulation during the study period with or without prior PrEP use.

(Obj 6) People without HIV in OPERA aged ≥ 18 years who could benefit from PrEP and are not on PrEP

Variables

Exposures:

- PrEP use (never, use within ≤ 12 months before diagnosis, use > 12 months before diagnosis)
- Time-updated PrEP type (oral or LA)

Outcomes:

- Incident HIV diagnosis: New HIV diagnosis *and/or* detectable HIV RNA *and/or* positive antigen/antibody test
- PrEP coverage: Proportion of days of access to oral PrEP or proportion of days of coverage by CAB LA
- HIV testing/STI screening: frequency and type of tests performed

Data Sources

OPERA cohort, a multi-site observational database built from the complete patient health records managed in electronic health record (EHR) systems throughout the US.

Study Size

Between 21DEC2021 and 30JUN2023 (Analysis # 1 inclusion period), 22,234 adults without HIV started a new PrEP formulation in OPERA. The first formulation used during the study period was TAF/FTC oral (n=12,110, 54%), TDF/FTC oral (n=9,740, 44%), or CAB LA (n=384, 2%). An additional 292 individuals switched to CAB LA PrEP later during the study period, for a total of 767 people receiving CAB LA injections during the Analysis #1 inclusion period.

Protocol for Non-Interventional Studies PASS Studies and Non-PASS Studies (4.0) March 2024

Template Doc ID: TMF-15706807

Parent Doc ID: VQD-SOP-066694

Data Analysis

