7. RESEARCH METHODS

7.1. Study Design

A cohort study using secondary data from the OPERA[®] (Observational Pharmacology Epidemiology Research & Analysis) cohort will be used to answer the study objectives. OPERA is a multi-site observational database collecting data prospectively from the complete electronic health records (EHR) from clinical care throughout the US.

[figure not shown]
Analyses to meet the study objectives will be conducted twice during the study period. Analysis #1 will include data from 01JAN2021-31DEC2023 (Obj. 1-1a) and from 21DEC2021 to 30JUN2024 (Obj 2-6). Analysis #2 will be a repeat of Analysis #1 with data from 1JAN2021-31DEC2024 (Obj. 1-1a) and from 21DEC2021 to 30JUN2025 (Obj 2-6). A

summary of the study design is provided in Table 1 (exposure groups, index date, censoring criteria, endpoints) and in Figure 1 (timeline).

Table 1. Summary of study design

		Analysis #1	Analysis #2
Obj 1 Among all people without HIV in OPERA	Exposure groups	Calendar years	Calendar years
	Index date	NA	NA
	Censoring criteria	NA	NA
	Endpoints	HIV diagnosis	HIV diagnosis
Obj 1a Among people with a new HIV diagnosis	Exposure groups	PrEP use (never, use within ≤12 months before diagnosis, use >12 months before diagnosis)	PrEP use (never, use within ≤12 months before diagnosis, use >12 months before diagnosis)
	Index date	Date of HIV diagnosis	Date of HIV diagnosis
	Censoring criteria	NA	NA
	Endpoints	NA	NA
Obj 2-5 Among PrEP users	Exposure groups	Oral PrEP, CAB LA PrEP	Oral PrEP, CAB LA PrEP
	Index date	Start of first PrEP regimen during the study period	Start of first PrEP regimen during the study period
	Censoring criteria	Death, loss to follow-up (12 months after last clinical contact), study end (30JUN2024), 12 months after index date	Death, loss to follow-up (12 months after last clinical contact), study end (30JUN2025), 12 months after index date
	Endpoints	HIV diagnosis, PrEP coverage, HIV testing, STI screening, STI diagnoses	HIV diagnosis, PrEP coverage, HIV testing, STI screening, STI diagnoses
Obj 6 Among people who could benefit from PrEP	Exposure groups	NA	NA
	Index date	First OPERA visit with indication for PrEP during study period	First OPERA visit with indication for PrEP during study period
	Censoring criteria	Death, loss to follow-up, study end (30JUN2024), 12 months after index date, PrEP initiation	Death, loss to follow-up, study end (30JUN2025), 12 months after index date, PrEP initiation

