	Endpoints	HIV testing, HIV diagnoses, STI screening, STI diagnoses	HIV testing, HIV diagnoses, STI screening, STI diagnoses

Figure 1. Study timeline

^a Inclusion dates: 1JAN202X to 31DEC202X of each year

^b Inclusion dates: 21DEC2021 to 30JUN2023, with potential follow-up through 30JUN2024

^c Inclusion dates: 21DEC2021 to 31JUN2024, with potential follow-up through 30JUN2025

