7.2. Study Population and Setting

7.2.1. Inclusion Criteria

People without HIV in OPERA (Obj 1)

- i. ≥ 1 clinical encounter in OPERA during the calendar year of interest
- ii. ≥ 18 years old at the first clinical encounter during the calendar year of interest
- iii. No evidence of prior HIV diagnosis

People with a new HIV diagnosis (Obj 1.a)

- i. Incident HIV diagnosis (new HIV diagnosis/positive HIV test/detectable HIV RNA viral load) identified in Obj 1

PrEP users (Obj 2-5)

- i. HIV-negative
- ii. ≥ 18 years of age
- iii. Started any new PrEP formulation
 - Analysis #1: between 21DEC2021 and 30JUN2023
 - Analysis #2: between 21DEC2021 and 30JUN2024
- iv. With or without prior PrEP use (a different formulation or a gap ≥ 61 days without any PrEP immediately prior to the index PrEP; the same formulation may have been used ≥ 61 days before starting the index PrEP)

People who could benefit from PrEP (Obj 6)

- i. HIV-negative
- ii. ≥ 18 years of age

- iii. ≥ 1 clinical encounter in OPERA during the inclusion period
 - Analysis #1: between 21DEC2021 and 30JUN2023
 - Analysis #2: between 21DEC2021 and 30JUN2024
- iv. Any of the following indications for PrEP¹¹:
 - Bacterial STI in past 12 monthsⁱ (gonorrhea, syphilis, chlamydia)⁷
 - Alcohol use disorder⁷
 - Illicit non-injection drug use⁷
 - Injection drug use^{7, 14}
 - Black women¹⁴
 - Transgender women¹⁴
 - Men who have sex with men¹⁴
 - All individuals aged 18-24 yearsⁱⁱ¹⁴
 - Any history of PrEP use

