- Crosstabulation of HIV and STI testing frequency
- STI diagnoses
 - New diagnosis of STI as noted in medical record or positive test result
 - STI diagnoses for
 - Syphilis
 - Gonorrhea
 - Chlamydia
 - Chancroid
 - Lymphogranuloma venereum
 - Mycoplasma genitalium
 - Hepatitis B virus (HBV)
 - Hepatitis C virus (HCV)
 - HSV-2
 - Trichomoniasis
 - HPV and/or genital warts

People who could benefit from PrEP (Obj 6)

HIV testing & STI screening

- HIV testing
 - Frequency and rate (per 100 person years) of HIV tests over 12-month period
 - Type of HIV tests (RNA [quantitative, qualitative], antigen/antibody, rapid screen)
 - HIV testing practices (type, frequency) by HCP type (MD or DO, physician associate, nurse practitioner, other/unknown)
 - HIV testing practices (type, frequency) by clinic type (healthcare center, wellness center, other)
- HIV diagnoses
 - Frequency of new HIV diagnosis and/or detectable HIV RNA and/or positive antigen/antibody test
 - Rate of incident HIV diagnoses per 100 person-years of follow-up
 - Within the first 12 months after index PrEP start
 - Through study end (Analysis #1: 30JUN2024; Analysis #2: 30JUN2025)

- Follow-up (FU) will be censored at first of:
 - HIV diagnosis
 - Death
 - Study end (Analysis #1: 30JUN2024; Analysis #2: 30JUN2025)
 - Loss to follow-up (12 months after last clinical contact)
 - 12 months after index date
- All potential HIV acquisitions will be subject to a thorough chart review for confirmation
 - All lab results, diagnoses, ART prescriptions and clinician notes available in OPERA on or after the potential HIV acquisition was identified will be reviewed
- STI screening
 - Frequency and rate (per 100 person years) of STI testing events (testing for multiple STIs on the same day will count as 1 testing event)
 - Type of other STI tests
 - Syphilis
 - Gonorrhea
 - Chlamydia
 - Chancroid
 - Lymphogranuloma venereum
 - Mycoplasma genitalium
 - Hepatitis B virus (HBV)
 - Hepatitis C virus (HCV)
 - HSV-2
 - Trichomoniasis
 - HPV and/or genital warts
 - Timing of STI tests as recommended by PrEP clinical guidelines⁷
 - Testing 3 months (76-104 days) after last test
 - Testing 6 months (168-196 days) after last test
 - Testing 12 months (351-379 days) after last test
 - STI screening practices (type, frequency) by HCP type type (MD or DO, physician associate, nurse practitioner, other/unknown)
 - STI screening practices (type, frequency) by clinic type (healthcare center, wellness center, other)

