	Oral PrEP N=	CAB LA PrEP N=
HIV testing on schedule (oral: every 3 months (76-104 days); CAB LA: ±14 days of each injection), n (%)		
STI screening every 3 months (76-104 days) ^c , n (%)		
STI screening every 6 months (168-196 days) ^d , n (%)		
STI screening every 12 months (351-379 days) ^e , n (%)		
HIV testing NOT on schedule (oral: every 3 months (76-104 days); CAB LA: ±14 days of each injection), n (%)		
STI screening every 3 months (76-104 days) ^c , n (%)		
STI screening every 6 months (168-196 days) ^d , n (%)		
STI screening every 12 months (351-379 days) ^e , n (%)		

\$(vault:document_date__v)

Protocol for Non-Interventional Studies PASS Studies and Non-PASS Studies (4.0) March 2024

Template Doc ID: TMF-15706807

Parent Doc ID: VQD-SOP-066694

Table 26. STI diagnoses among PrEP users^a

	Oral PrEP N=	CAB LA PrEP N=
STI diagnosis within 14 days before/on day of PrEP type start, n (%)		
Any, n (%)		
Syphilis, n (%)		
Gonorrhea, n (%)		
Chlamydia, n (%)		
Chancroid, n (%)		
Lymphogranuloma venereum, n (%)		
Mycoplasma genitalium, n (%)		
Herpes Simplex-2, n (%)		
Trichomoniasis, n (%)		
Human papilloma virus/genital warts, n (%)		
HBV, n (%)		
HCV, n (%)		
STI diagnosis within 12 months after PrEP type start, n (%)		
Any, n (%)		
Syphilis, n (%)		
Gonorrhea, n (%)		
Chlamydia, n (%)		
Chancroid, n (%)		
Lymphogranuloma venereum, n (%)		
Mycoplasma genitalium, n (%)		
Herpes Simplex-2, n (%)		
Trichomoniasis, n (%)		
Human papilloma virus/genital warts, n (%)		
HBV, n (%)		
HCV, n (%)		

^a Tests are only counted for the PrEP type used at the time of diagnosis

Table 27. Incidence rate of STI diagnoses within 12 months of index among PrEP users^a

	Oral PrEP N=	CAB LA PrEP N=
Total # STI diagnoses within 12 months of index, n		
Person-years of follow-up		
IR per 100 py (95% CI)		

Table 28. Identification of the people who could benefit from PrEP population

	Included N (%)	Excluded N (%)
All individuals in OPERA		
≥1 clinical encounter between 21DEC2021 and 30JUN2023		
≥18 years old at first clinical encounter in study period		
Any indication for PrEP ^a		
No PrEP use between 21DEC2021 and 30JUN2023		

^a Bacterial STI in past 12 months (gonorrhea, syphilis, chlamydia), alcohol use disorder, illicit non-injection drug use, injection drug use. Black woman, transgender woman, men who have sex with men, aged 18-24 years, any history of PrEP use

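### Annex 1 Table 28 excludes Objective 6 subjects for PrEP started after their index visit, while Table 1 of Section 7.1 censors at PrEP initiation; one rule, based on status at index, is needed

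*Protocol*

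**What the plan says.** The protocol handles PrEP use in the Objective 6 population in five places.

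- **Synopsis and Objective 6.** The population is people "who could benefit from PrEP and are not on PrEP", with no time point attached.
- **Section 7.2.1.** The Objective 6 criteria (HIV-negative, adult, an encounter in the window, an indication) contain no PrEP-status criterion. One indication is "Any history of PrEP use". The window is "Analysis #1: between 21DEC2021 and 30JUN2023".
- **Section 7.1, Table 1.** Index is "First OPERA visit with indication for PrEP during study period". The Analysis #1 censoring criteria are "Death, loss to follow-up, study end (30JUN2024), 12 months after index date, PrEP initiation".
- **Section 7.3.2.** For Objective 6 HIV diagnoses, the list introduced by "Follow-up (FU) will be censored at first of" names HIV diagnosis, death, study end, loss to follow-up and 12 months after index. PrEP initiation is not on it.
- **Annex 1, Table 28.** The last selection row is "No PrEP use between 21DEC2021 and 30JUN2023". No row requires the person to be HIV-negative.

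The notes to Figure 1 give "Inclusion dates: 21DEC2021 to 30JUN2023, with potential follow-up through 30JUN2024" for Analysis #1. Annex 1 states that the shells carry over to Analysis #2 with updated periods.

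**The concern.** Index can fall anywhere in the window, but the Table 28 row covers all of it. Whether a person counts in the Objective 6 denominator therefore depends in part on what happens after time zero. A person who starts PrEP after index was under observation, off PrEP and free of diagnosed HIV up to that start. Censoring keeps this time; Table 28 deletes it. Diagnoses in people who never start PrEP all stay.

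The HIV rate among people not on PrEP would then be too high as far as these people are concerned. Section 5 states that an HIV test is required before PrEP initiation, so dropping starters also drops tests and probably lowers the HIV testing rate. Objective 6 is one of the primary objectives, and Section 7.7.1.1 plans Poisson-estimated rates for it, so the choice of rule affects reported results.

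**Working it through.** **1. Window against follow-up.** From 21DEC2021 to 30JUN2023, both days included, is 557 days (557/365.25 = 1.525 years, 18.3 months). Follow-up is 12 months. A person indexed on 21DEC2021 can complete 12 months without PrEP and still be excluded for starting in the following six months. With the Analysis #2 window ending 30JUN2024 there are 923 days (2.527 years).

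**2. The same event under each text (Analysis #1).**

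| PrEP start, within 12 months of index | Table 28 | Table 1, Section 7.1 | Section 7.3.2 HIV list |
|---|---|---|---|
| After index, by 30JUN2023 | Person excluded | Censored at start | Not mentioned |
| After 30JUN2023 | Person kept | Censored at start | Not mentioned |

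If Tables 1 and 28 are applied together, a start on 30JUN2023 removes the person and a start on 01JUL2023 only ends follow-up. In Analysis #2 the second start also leads to exclusion, so people counted in Analysis #1 can drop out.

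**3. Size for post-index starters.** The protocol states no Objective 6 count or rate, so there is no figure to reproduce. Assumptions: a constant PrEP-start rate λ per person-year, a low HIV rate independent of it, 12 months of follow-up, and index dates uniform over a window of W years. All HIV events before PrEP are kept, so

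inflation of the HIV rate = person-time under censoring ÷ person-time left by Table 28.

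- Under censoring, per person: T = (1 − e^(−λ))/λ.
- Left by Table 28, per person: K = [2(1 − e^(−λ)(1+λ))/λ² + (e^(−λ) − e^(−λW))/λ]/W.

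For λ = 0.10 and W = 1.525: T = 0.9516, K = (0.9358 + 0.4628)/1.525 = 0.9171, and T/K = 1.038.

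| λ (assumed) | Analysis #1, W = 1.525 | Analysis #2, W = 2.527 |
|---|---|---|
| 0.05 | 0.9754/0.9575 = 1.019 | 0.9754/0.9362 = 1.042 |
| 0.10 | 0.9516/0.9171 = 1.038 | 0.9516/0.8774 = 1.085 |
| 0.20 | 0.9063/0.8421 = 1.076 | 0.9063/0.7730 = 1.172 |
| 0.36 | 0.8398/0.7366 = 1.140 | 0.8398/0.6367 = 1.319 |

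A simulation with an HIV rate of 1 per 100 person-years gives the same Analysis #1 ratios (1.019, 1.038, 1.076, 1.140). It excludes 3.7% to 23.0% of people and loses 1.8% to 12.3% of person-time. People indexed on the first day of the window are the extreme case, with inflation of about 5% to 45%.

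**4. A count-based check.** Give each kept person one year. With 150,000 eligible, of whom 8,000 start after 3 months: (142,000 + 2,000)/142,000 = 1.014. With 100,000 eligible, of whom 10,000 start after 4 months: (90,000 + 3,333)/90,000 = 1.037. These counts are also assumptions.

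**5. HIV testing.** Assume one background test per person-year plus one at PrEP start. Over the same range of λ, the simulated rate falls from 105, 110, 120 and 136 per 100 person-years under censoring to 102, 103, 107 and 113 under exclusion.

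**The case against.** **The tables do not flatly contradict each other.** Table 1 sets index and censoring, not eligibility, and its PrEP censoring still has work to do after 30JUN2023. This stands. But the combination makes the consequence of a PrEP start depend on its calendar date, and it still selects on a post-index event.

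**The exclusion is one row in an empty shell.** Neighbouring Objective 6 shells show carry-over from the PrEP-user tables: Table 35 has an oral PrEP column and Table 43 has oral and CAB LA columns. The row therefore does not prove that this rule will be run. It is, however, the only place where being off PrEP is turned into a selection step, so a programmer would have to follow it.

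**Section 7.3.2 is probably not a deliberate third rule.** Its Objective 6 text also counts from an index PrEP start, which these people do not have. The omission looks copied, but it still needs correcting.

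**A reader might infer that the HIV rate must be biased upward because nobody with a diagnosis can be removed.** The documents do not support that. Table 28 bars any PrEP use in the window, including use before index. Someone who stopped PrEP early in 2022, was indexed later because of that history, and was then diagnosed would be excluded along with the event.

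**A reader might anchor the size on the 22,234 people who started a formulation in the window.** That count includes direct switches between formulations and people who may have had no earlier indicated visit. Taking 15,000 starters among only 60,000 eligible, each after 6 months, gives (45,000 + 7,500)/45,000 = 1.167, but nothing in the protocol supports those counts. Table 2 of Section 7.4 shows 294,314 active people without HIV, so 60,000 eligible looks low. With 100,000 eligible the same starters give (85,000 + 7,500)/85,000 = 1.088.

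**A reader might treat Objective 6 as a comparator for the PrEP users.** The protocol describes itself as descriptive and plans no such comparison. The concern is with the Objective 6 rates themselves.

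**Conclusion.** The point holds. Table 28 as written selects on an event after time zero, and it is not aligned with Sections 7.1, 7.2.1 and 7.3.2. For people who start PrEP after index, the effect is to raise the HIV rate and probably to lower the HIV testing rate. For the row as a whole, the net direction is not fully established, because people with PrEP use in the window before index are removed as well.

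The size is unknown from the documents. Under the assumptions shown, it runs from about 1–2% to the low teens in Analysis #1 with index dates spread over the window, and grows with the longer window of Analysis #2. These figures depend on the assumed start rates and on PrEP starters having the same HIV risk as others; a different risk would change them. Because the row states a biasing rule and leaves the Objective 6 cohort ambiguous, it should be settled before Analysis #1 is programmed.

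**What to change.** 1. Replace the last row of Annex 1 Table 28 with 'Not on PrEP at the index visit', defined only from data at or before index. The 61-day gap that Section 7.2.1 already uses for PrEP users could serve as the definition.
2. Add the same criterion to the Objective 6 list in Section 7.2.1.
3. Add PrEP initiation to the Objective 6 censoring list in Section 7.3.2, and apply it to HIV testing, HIV diagnoses, STI screening and STI diagnoses alike, in agreement with Table 1 of Section 7.1.
4. Add to Table 28 the HIV-negative step that Section 7.2.1 requires.

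The cost is wording and programming. No new data are needed. The cohort gains the post-index starters, and later starts no longer remove people already counted in Analysis #1 from Analysis #2.
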